10.5 Serious Adverse Events

Any adverse Event that meets any of the following criteria: (1) results in death; (2) is life-threatening (i.e. places a participant at immediate risk of death from the event as it occurred); (3) requires inpatient hospitalization or prolongation of existing hospitalization; (4) results in a persistent or significant disability/incapacity; (5) results in a congenital anomaly/birth defect; OR (6) any other adverse event that, based upon appropriate medical judgment, may jeopardize the participant's health and may require medical or surgical intervention to prevent one of the other outcomes listed in this definition (e.g. allergic bronchospasm requiring intensive treatment in the emergency room or at home).

Information about all serious adverse events, whether volunteered by the subject, discovered by investigator questioning, or detected through physical examination, laboratory test or other means, will be collected and recorded on the Serious Adverse Event eCRF.

For this study, all SAEs occurring from the time of drug administration to 30 days post-study completion visit will be captured on the SAE eCRF. As the Month 36 Visit is a Phone Call Visit, review of subjects' medical records is required, in order to evaluate any SAEs within 30 days post-study completion visit. Unless exempted as described below, all SAEs, whether or not deemed drug-related, must be reported by the investigator or qualified designee within 1

business day of first becoming aware of the event. The investigator/qualified designee will enter the required information regarding the SAE into the appropriate module of the IBM Clinical Development, which will automatically result in distribution of the information to the Duke Clinical Research Institute Medical Monitor and Clinical Operations team, and the Network Management Core (NEMO). If IBM Clinical Development is temporarily unavailable, the event, including the investigator-determined causality to study drug, should be reported via a paper back-up SAE form to the DCRI Medical Monitor and Clinical Operations team, and the NEMO. Upon return of the availability of EDC system, the SAE information must be entered into the eCRF.

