13.2 Statistical Monitoring Plan

Safety and efficacy data will be periodically assessed by the DSMB. Safety and efficacy data will be periodically assessed by the DSMB. For ethical reasons, an interim examination of key safety and endpoint data will be performed at regular intervals during the course of the trial. The interim monitoring will also involve a review of the control arm event rates, patient recruitment, compliance with the study protocol, status of data collection, and other factors that reflect the overall progress and integrity of the study. An NHLBI-appointed DSMB will carefully and confidentially review the results of the interim analyses and status reports. If protocol modifications are warranted, close consultation among the DSMB, the NHLBI staff, and the study leadership will be required. A separate DSMB charter outlining the operating guidelines for the committee and the protocol for evaluation of data will be created prior to study enrollment and agreed upon during the initial meeting of the DSMB.

It is anticipated that the DSMB will meet at 6-month intervals to review the accumulating data. The DCRI will create regular reports to track patient enrollment reports, rates of compliance with the assigned testing strategy, and frequency of protocol violations. Prior to each meeting, the data coordinating center will conduct any requested statistical analyses and prepare a summary report along with the following information: patient enrollment reports, rates of compliance with the assigned testing strategy, frequency of protocol violations, and description of SAEs (statistical comparisons of the randomized arms with respect to these SAEs will use chi-square or other appropriate 2-sample methods).

There will be one planned interim review for efficacy. The efficacy review will focus on the composite endpoint of respiratory hospitalization or all-cause death and should occur once 300 enrolled subjects have been followed for 12 months. The Lan-DeMets alpha spending function with O'Brien-Fleming type boundaries will be used for the interim analysis.

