## IV. General Methodology

---

Definition of Statistical Significance: The statistical plan will test non-directional hypotheses, i.e., all tests will be 2-sided. The level of significance for all efficacy and safety analyses will be 0.05.

Statistical Tests: For situations where one observation per patient is observed, (e.g. safety comparisons at individual time points), a general analysis convention will be used unless otherwise specified. For continuous and ordinal variables, treatment group differences will be tested using the Wilcoxon rank-sum test for two groups and Kruskal-Wallis one-way analysis of variance for comparisons of more than two groups. For censored data, like time to event, treatment group differences will be tested using the log rank test. For discrete variables, treatment group differences will be tested using the chi-square test. In the situation of low cell counts the treatment group differences will be tested using Fisher's exact method.

Descriptive Statistics: For continuous and ordinal variables the number of observations, number of missing values, mean, standard deviation, median, twenty-fifth percentile, and seventy-fifth percentile will be given. For binary (e.g. yes/no), categorical, and/or ordinal variables a simple count and percent will be provided. Other statistics may be considered if necessary.

Descriptive Plots: Descriptive plots may be produced in addition to descriptive statistics if deemed appropriate. If deemed necessary plots of descriptive statistics such as spaghetti, mosaic, box, cumulative distribution, and loess curves will be provided.

Study Listings: Study data will be listed by treatment group, visit if applicable, and patient where appropriate.

Software and Validation Procedures: All data presented in interim and final analyses will be generated and validated under the guidance of the DCRI Clinical Trials Statistical SOPs.

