### **Serious adverse events**

Endpoint Description: Frequency and types of serious adverse events (SAEs) during the following-up period of the trial.

Response Variable Definition: SAEs will be identified by the site PI and coded into the MEDRA medical dictionary.

Statistical Tests: The number of patients with one or more SAEs will be tabulated along with the total number of distinct SAEs. Comparison of the “Standard care + oral antimicrobial therapy” and “Standard care” arms will be done with a chi-square test, i.e. the number of patient with one or more events. Other groupings of SAEs maybe generated as deemed necessary.

Interpretation of Results: For cases where “Standard care + oral antimicrobial therapy” rate is less than “Standard care” rate will indicate a reduction for “Standard care + oral antimicrobial therapy” arm. For cases where “Standard care + oral antimicrobial therapy” rate is greater than “Standard care” rate will indicate an increase for “Standard care + oral antimicrobial therapy” arm.

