Summarization format NPAT (xx.x%) NSAE, where NPAT is the number of patient with at least one SAE, xx.x% = NPAT divided by the total number of randomized patients times 100, and NSAE is the number of SAEs observed

**CLEANUP-IPF Study  
Final Analysis Table 5.2  
Safety  
Concomitant Medications Shift Table**

Parameter	Baseline Usage	Post-Baseline Usage	Oral antimicrobial therapy N= NEVAL	Standard Care N= N EVAL	All Patients N= N EVAL
PPI					
	No	No	N/N (xx.x%)	N/N (xx.x%)	N/N
		(xx.x%) Yes	N/N (xx.x%)	N/N (xx.x%)	N/N (xx.x%)
	Yes	No	N/N (xx.x%)	N/N (xx.x%)	N/N
		(xx.x%) Yes	N/N (xx.x%)	N/N (xx.x%)	N/N (xx.x%)
	Overall	No	N/N (xx.x%)	N/N (xx.x%)	N/N
		(xx.x%) Yes	N/N (xx.x%)	N/N (xx.x%)	N/N (xx.x%)
H2 Blocker					
	No	No	N/N (xx.x%)	N/N (xx.x%)	N/N (xx.x%)
		Yes	N/N (xx.x%)	N/N (xx.x%)	N/N (xx.x%)
	Yes	No	N/N (xx.x%)	N/N (xx.x%)	N/N (xx.x%)
		Yes	N/N (xx.x%)	N/N (xx.x%)	N/N (xx.x%)
	Overall	No	N/N (xx.x%)	N/N (xx.x%)	N/N (xx.x%)
		Yes	N/N (xx.x%)	N/N (xx.x%)	N/N (xx.x%)
Chronic prednisone					
	No	No	N/N (xx.x%)	N/N (xx.x%)	N/N (xx.x%)
		Yes	N/N (xx.x%)	N/N (xx.x%)	N/N (xx.x%)
	Yes	No	N/N (xx.x%)	N/N (xx.x%)	N/N (xx.x%)
		Yes	N/N (xx.x%)	N/N (xx.x%)	N/N (xx.x%)
	Overall	No	N/N (xx.x%)	N/N (xx.x%)	N/N (xx.x%)
		Yes	N/N (xx.x%)	N/N (xx.x%)	N/N (xx.x%)
Azathioprine					
	No	No	N/N (xx.x%)	N/N (xx.x%)	N/N (xx.x%)
		Yes	N/N (xx.x%)	N/N (xx.x%)	N/N (xx.x%)
	Yes	No	N/N (xx.x%)	N/N (xx.x%)	N/N (xx.x%)
		Yes	N/N (xx.x%)	N/N (xx.x%)	N/N (xx.x%)
	Overall	No	N/N (xx.x%)	N/N (xx.x%)	N/N (xx.x%)
		Yes	N/N (xx.x%)	N/N (xx.x%)	N/N (xx.x%)
NAC					

**CLEANUP-IPF Study  
Final Analysis Table 5.2  
Safety  
Concomitant Medications Shift Table**

Parameter	Baseline Usage	Post-Baseline Usage	Oral antimicrobial therapy N= N EVAL	Standard Care N= N EVAL	All Patients N= N EVAL	
Cotrimoxazole	No	No	N/N (xx.x%)	N/N (xx.x%)	N/N (xx.x%)	
		Yes	N/N (xx.x%)	N/N (xx.x%)	N/N (xx.x%)	
	Yes	No	N/N (xx.x%)	N/N (xx.x%)	N/N (xx.x%)	
		Yes	N/N (xx.x%)	N/N (xx.x%)	N/N (xx.x%)	
	Overall	No	N/N (xx.x%)	N/N (xx.x%)	N/N (xx.x%)	
		Yes	N/N (xx.x%)	N/N (xx.x%)	N/N (xx.x%)	
	MDI	No	No	N/N (xx.x%)	N/N (xx.x%)	N/N (xx.x%)
			Yes	N/N (xx.x%)	N/N (xx.x%)	N/N (xx.x%)
Yes		No	N/N (xx.x%)	N/N (xx.x%)	N/N (xx.x%)	
		Yes	N/N (xx.x%)	N/N (xx.x%)	N/N (xx.x%)	
Overall		No	N/N (xx.x%)	N/N (xx.x%)	N/N (xx.x%)	
		Yes	N/N (xx.x%)	N/N (xx.x%)	N/N (xx.x%)	

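### Serious adverse events are compared by an ever/never chi-square that ignores unequal follow-up: a moderate loss of power, and bias if withdrawal differs by arm

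*SAP*

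**What the plan says.** The SAE entry in SAP section IX plans two summaries: "The number of patients with one or more SAEs will be tabulated along with the total number of distinct SAEs". The between-arm test uses the first of these: "arms will be done with a chi-square test, i.e. the number of patient with one or more events". The footnote to mock-up Table 5.1 fixes the denominator: "xx.x% = NPAT divided by the total number of randomized patients times 100". SAP section IV sets the level: "The level of significance for all efficacy and safety analyses will be 0.05". The 2020 addendum changes how SAEs are coded but not how the arms are compared.

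Three other places bear on the point:

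- Protocol section 10.5 counts as serious any adverse event that results in death or "requires inpatient hospitalization or prolongation of existing hospitalization". Capture runs from drug administration to 30 days after the completion visit.
- Follow-up varies between patients. Protocol section 8 sets a maximum of 36 months. Section 11.3 sets a minimum of 12 months but a maximum of 42, which has to be reconciled with section 8. After the December 2019 termination, last visits were to take place by mid-March 2020.
- SAP section IV has a general convention: "For censored data, like time to event, treatment group differences will be tested using the log rank test". Section IX does not use it for SAEs.

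**The concern.** An ever/never comparison discards the timing of events and the time each patient was observed. A patient who withdraws at two months without an SAE counts the same as one followed SAE-free for three years. With common events and long follow-up, many patients in both arms reach a first SAE, and the two proportions draw together even when the hazards differ.

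The comparison matters because the trial gives long-term antimicrobials open-label, so intolerance or knowledge of the assignment could make withdrawal differ by arm. If patients on antimicrobials left earlier, they would have less time in which to record an SAE, and the crude percentage would lean towards no harm. The close-out letter mentions a trend towards more SAEs in the intervention arm, so how this comparison is made has practical weight.

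**Working it through.** **Inputs from the documents.** 500 patients randomized 1:1 (taken as 250 per arm), 30 months of accrual, minimum follow-up 12 months, dropout about 2% a year, exponential event times, two-sided 0.05. The 12-month control rates for the primary endpoint are 24% to 36% (protocol section 11.3), and the 36-month cap is from protocol section 8.

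**Assumptions.** The documents give no SAE rate. I use 24% and 36% as an approximate floor, and 50% to show the direction. The SAE hazard ratios and unequal withdrawal rates are also assumed.

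**Check of the set-up.** With the power section's 12 to 42 months, the first row of protocol Table 1 (24% against 16.8%) gives a hazard ratio of 0.670 and 192 events. Power is 79.1% by Schoenfeld's formula and 78.0% by Freedman's, against 78% stated. All nine rows agree within 2 points.

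**Share of patients with an SAE.** With SAE hazard λ = −ln(1 − 12-month rate) and dropout hazard δ = −ln(0.98), the expected share p is the average of λ/(λ+δ) × [1 − exp(−(λ+δ)T)]. T is uniform from 1 to 3.5 years, capped at 3. Call it p0 in control and p1 under hazard HR × λ.

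**Efficiency at a true HR of 1.3.**

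- Chi-square: z = (p1 − p0) / √[2p̄(1 − p̄)/250], where p̄ is the mean of p0 and p1.
- Log-rank: z = ln(HR) × √D / 2, with D = 250(p0 + p1).
- Power is Φ(z − 1.96). Relative efficiency is the squared ratio of the two z values.

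| 12-month SAE rate | p0 | p1 | z, chi-square | z, log-rank | Power, chi-square | Power, log-rank | Efficiency |
|---|---|---|---|---|---|---|---|
| 24% | 0.435 | 0.521 | 1.91 | 2.03 | 48% | 53% | 0.89 |
| 36% | 0.597 | 0.688 | 2.10 | 2.35 | 56% | 65% | 0.80 |
| 50% (assumed) | 0.746 | 0.824 | 2.11 | 2.60 | 56% | 74% | 0.66 |

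The loss is therefore 11% to 20% at the documented rates and about one third at 50%.

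**Loss near the null.** The limit is 1 − (dp/d ln λ)² / [p²(1 − p)]. It gives 8.9% at the 24% rate, 16.5% at 36% and 28.7% at 50%. With a 42-month maximum the range for 24% to 36% is 10% to 18%. With an assumed 3 to 30 months after early close-out it is 10% to 16%. At SAE rates of 15% or less it is below 5%.

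**Bias from unequal withdrawal.** Same formula, 36% rate, true HR 1.25, control withdrawal 2% a year (p0 = 0.597):

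| Withdrawal per year, antimicrobial arm | p1 | Crude difference |
|---|---|---|
| 2% | 0.674 | +7.7 points |
| 3% | 0.668 | +7.1 points |
| 5% | 0.656 | +5.9 points |
| 10% | 0.626 | +2.9 points |

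Reversing the last row (10% in control, 2% on antimicrobials) gives 0.674 − 0.552 = +12.2 points, so the bias can also exaggerate harm.

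**Simulation (6,000 trials, 30% rate).** With equal withdrawal the chi-square keeps its level. At a true HR of 1.4, it detects harm in 75% of trials and the log-rank in 82%. With 5% against 2% a year the figures are 61% and 81%; with 10% against 2% they are 35% and 79%. With no true effect and 10% against 2%, the chi-square shows a significant SAE reduction in 15.6% of trials, where 2.5% is nominal.

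**The case against.** The strongest reply is that much of the harm is already analysed with censoring. The SAP has Cox models for death, for first non-elective respiratory hospitalization and for first non-elective all-cause hospitalization, all two-sided, with a hazard ratio above 1 read as an increase on antimicrobials. Kaplan-Meier withdrawal rates by arm are planned (Table 1.2, Graph 1.2.1), so unequal loss would be visible. This stands as partial mitigation. But the Cox models leave out other SAEs, and the withdrawal curves show a problem without correcting the SAE percentages.

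It can also be said that the bias is hypothetical. That is fair: the only documented dropout figure is about 2% a year, and at 3% against 2% the shift is 0.6 points (7.7 − 7.1).

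Three stronger readings are tempting, and the documents do not support them:

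- A reader might infer that section IX contradicts section IV. The log-rank convention is a default that gives way where another test is specified, and section IX specifies one. It is a weak choice, not an inconsistency.
- A reader might infer that the monitoring board is tied to the same test. Protocol section 13.2 is wider: "statistical comparisons of the randomized arms with respect to these SAEs will use chi-square or other appropriate 2-sample methods". A log-rank test is a two-sample method. The board also noted the SAE trend, so it was not hidden from it.
- A reader might infer that variable follow-up by itself biases the comparison. Randomization balances entry time, so it costs only efficiency.

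**Conclusion.** The point holds, with a moderate size. The only planned between-arm SAE test ignores follow-up time. At 12-month rates of 24% to 36% the loss against a log-rank test is about 11% to 20% at a hazard ratio of 1.3, or 5 to 9 points of power, and 9% to 17% near the null. This rests on the primary-endpoint rates standing in for an undocumented SAE rate, on exponential event times and on planned follow-up.

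A reader might put the loss at 20% to 35%. Near the null that needs a 12-month SAE rate of about 40% to 56%, for which the documents give no source. Nor do most patients necessarily have an SAE: the expected control share is 44% at the 24% rate, though 60% at 36%.

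Possible bias is the weightier reason to change the plan. It depends entirely on withdrawal differing by arm, can go either way, and is small unless the difference is marked.

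**What to change.** In SAP section IX, make the between-arm SAE comparison time from randomization to first SAE: Kaplan-Meier cumulative risk by arm, a log-rank test, and a Cox hazard ratio with 95% confidence interval, censored at the end of SAE follow-up. Death is itself an SAE, so it does not compete with the event. Report total SAEs per 100 patient-years by arm, and keep the Table 5.1 counts and percentages as description.

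Two details need settling first:

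- **Start of capture.** Protocol section 10.5 opens SAE capture at drug administration, an event that standard-care patients do not have. One start of capture, defined the same way for both arms, is needed.
- **Onset dates.** Protocol section 10.4 promises start and stop dates for adverse events of special interest. Section 10.5 does not list an onset date for SAEs, so confirm that the SAE form holds one.

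Protocol section 13.2 already permits the method in monitoring reports. The cost is SAP wording, one program and one more table. The log-rank test still assumes that withdrawal is unrelated to SAE risk, so the planned withdrawal curves should be read beside it.

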### **Concomitant Medication**

Endpoint Description: Frequency and types of concomitant medication usage during the following-up period of the trial.

Response Variable Definition: Concomitant medication will be collected each visit and phone contact with the site.

Statistical Tests: The number of patients with one or more given concomitant medication will be tabulated. Shift tables from baseline will be generate also. Comparison of the “Standard care + oral antimicrobial therapy” and “Standard care” arms will be done with a chi-square test, i.e. the number of patient with one or more occurrences. Other groupings of concomitant medication maybe generated as deemed necessary.

Interpretation of Results: For cases where “Standard care + oral antimicrobial therapy” rate is less than “Standard care” rate will indicate a reduction for “Standard care + oral antimicrobial therapy” arm. For cases where “Standard care + oral antimicrobial therapy” rate is greater than “Standard care” rate will indicate an increase for “Standard care + oral antimicrobial therapy” arm.

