5.2 Blinding

This study will be unblinded. Blinding would add substantial additional complexity without commensurate incremental benefit related to testing the primary hypothesis of a treatment strategy trial.

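### The only between-arm test of concomitant medication ignores baseline use, and the shift table that separates starts from stops carries no between-arm estimate or test

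*SAP*

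**What the plan says.** SAP section IX, Concomitant Medication, defines the endpoint as "Frequency and types of concomitant medication usage during the following-up period of the trial". The arms are compared on the "arms will be done with a chi-square test, i.e. the number of patient with one or more occurrences". The test has no stratification, adjustment or restriction by baseline use.

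The same paragraph adds "Shift tables from baseline will be generate also". The mock-up, Final Analysis Table 5.2 ("Concomitant Medications Shift Table"), cross-tabulates baseline use (No, Yes, Overall) by post-baseline use (No, Yes) within each arm. It covers nine drugs or classes: PPI, H2 blocker, chronic prednisone, azathioprine, NAC, co-trimoxazole, MDI, pirfenidone and nintedanib. It has no P-Value column, unlike the serious adverse event table (Table 5.1). Anything further is left open: "Other groupings of concomitant medication maybe generated as deemed necessary".

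SAP section IV sets the test conditions: "all tests will be 2-sided" and "The level of significance for all efficacy and safety analyses will be 0.05". On masking, Protocol 5.2 states "This study will be unblinded".

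**The concern.** What treatment assignment can change is whether a patient starts or stops a drug after randomization. Any use during follow-up mixes that change with use that was already there. For a drug many patients take at entry, users who simply continue add the same share to both arms and shrink the contrast being tested. The baseline value that would remove this is already collected, and Table 5.2 already splits patients by it, but the planned test does not use it.

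In an open-label trial, readers will want to know whether the arms diverged in other treatment, for example in pirfenidone, nintedanib or prednisone. No other planned analysis tests this. The compliance and crossover sections each describe one arm and plan no test, and Table 2.3 compares use at baseline only.

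**Working it through.** **Inputs from the documents.** About 500 patients (SAP section I) at 1:1 (Protocol 5.1), so 250 per arm; two-sided 0.05 (SAP section IV). The plan states no power for this test, so there is no figure to reproduce. The same N, allocation and alpha do reproduce the primary-endpoint power in Protocol Table 1 (78.2% to 98.2% recomputed, 78% to 98% printed).

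**Assumptions.** The documents give no usage rates. Let b be the share using the drug at baseline, s the share of baseline non-users who start, and c the share of baseline users who continue. The main case is s = 30% v 15% with c = 1.

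**Contrast tested.** Any use = b·c + (1 − b)·s. If c is the same in both arms, the difference in any use is (1 − b) times the difference in starts.

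**Power.** Φ[(d − 1.96·SE0)/SE1], where d is the difference in proportions, SE0 = √(2·p̄(1 − p̄)/n) and SE1 = √((p0(1 − p0) + p1(1 − p1))/n).

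Worked at b = 50%:

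- Planned test, n = 250: 0.5 + 0.5 × 0.15 = 57.5% v 0.5 + 0.5 × 0.30 = 65.0%. d = 0.075, SE0 = 0.0436, SE1 = 0.0434; (0.075 − 0.0855)/0.0434 = −0.24; power 41%.
- New starts among baseline non-users, n = 125: 15% v 30%. d = 0.15, SE0 = 0.0528, SE1 = 0.0520; (0.15 − 0.1035)/0.0520 = 0.89; power 81%.

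| Baseline use | Any use, by arm | Power, planned test | Non-users per arm | Power, new starts |
|---|---|---|---|---|
| 0% | 15.0 v 30.0% | 98% | 250 | 98% |
| 10% | 23.5 v 37.0% | 91% | 225 | 97% |
| 30% | 40.5 v 51.0% | 65% | 175 | 92% |
| 50% | 57.5 v 65.0% | 41% | 125 | 81% |
| 70% | 74.5 v 79.0% | 22% | 75 | 60% |
| 80% | 83.0 v 86.0% | 15% | 50 | 43% |

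**Other assumed rates.** With starts of 20% v 10%, the planned test has 66%, 36%, 20% and 12% power at baseline use of 10%, 30%, 50% and 70%, against 85%, 75%, 60% and 40% for new starts. Power of the planned test falls below 50% at baseline use of about 19% for starts of 20% v 10%, about 42% for 30% v 15%, and about 59% for 30% v 10%.

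**Opposite changes.** Let b = 50%, and let one arm have both more starts (20% v 10%) and more stops (20% v 10%). Any use is 0.5 × 0.8 + 0.5 × 0.2 = 50% in that arm and 0.5 × 0.9 + 0.5 × 0.1 = 50% in the other. The planned test then rejects only at its 5% error rate. Separate tests of starts and of stops, each with 125 per arm, have about 60% power.

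**Validity.** In simulation the type I error of the planned test stays near 5%. The loss is in power only.

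**The case against.** The strongest reply is that baseline use is not disregarded. The shift table is planned in the same paragraph as the test, and anyone reading Table 5.2 would see new starts of 30% v 15% directly. The SAP also allows other groupings and lets the templates be modified. This stands as far as display goes. What is missing is a pre-specified between-arm estimate or test on those rows, and the extra groupings are discretionary.

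Second, this is a safety summary in an intention-to-treat strategy trial. The SAP never calls it a check for co-treatment bias, and no primary result depends on its p-value. Antimicrobial use in the standard-care arm, the co-treatment that most directly dilutes the contrast, has its own crossover summary and an alternative analysis that censors at crossover. That stands and limits the importance of the point.

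A reader might infer two stronger things:

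- **That real differences would usually be missed.** The documents do not support this. It depends on baseline prevalence and the size of the difference, and neither is given. At 30% baseline use the main case still has 65% power. Azathioprine is excluded at entry (Protocol 4.2), and recent antimicrobial treatment is excluded too, so the azathioprine row and largely the co-trimoxazole row should lose little.
- **That chance baseline imbalance under simple randomization makes the test defective.** It does not. That variation is already inside the variance of a valid 5% test. The primary Cox model in the SAP also adjusts for NAC and standard-of-care medications at enrollment.

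**Conclusion.** The point holds as an inexpensive improvement to a valid secondary safety analysis. The only planned test is not conditioned on baseline use, and the table that is conditioned on it has no inference. For drugs common at baseline the cost in power is large: 41% instead of 81% at 50% baseline use in the main case. For drugs rarely used at baseline it is close to nothing. When starts and stops both rise in one arm, the planned test can be blind to the change.

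The sizes rest on assumed rates and on 250 per arm. The trial closed early, and the documents do not give the final number randomized; a smaller number would lower every power shown.

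**What to change.** In SAP section IX, Concomitant Medication, replace the test sentence with: For each medication, arms are compared on starts among patients not using it at baseline and, separately, on stops among patients using it at baseline. Each comparison is reported as a difference in proportions with a 95% confidence interval and a chi-square or Fisher p-value labelled nominal. Total use during follow-up is descriptive.

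Add the difference, interval and nominal p-value to the baseline No and baseline Yes rows of Table 5.2.

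A Cochran-Mantel-Haenszel test stratified by baseline use should not be offered as equivalent. It pools the two strata, so more starts and more stops in the same arm cancel. In the opposite-changes example its simulated power is 5%, against about 60% for each separate test.

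The cost is one sentence and extra columns in a planned table, with no new data. There are two drawbacks. Nine drugs with two comparisons each give about 18 nominal tests, or about 18 × 0.05 = 0.9 expected false positives, so the intervals should carry the interpretation. Power for starts also remains modest when baseline use is very high (60% at 70% and 43% at 80% in the main case).
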